10.1.2 Analysis Sets

10.1.2.1 Full Analysis Set

The full analysis set will consist of all enrolled subjects. Analyses for demographics and baseline characteristics will use this analysis set.

10.1.2.2 Safety Analysis Set

The safety analysis set will consist of all subjects who receive at least 1 dose of romiplostim. The analyses of all safety endpoints will be based on the safety analysis set.

10.1.2.3 Efficacy Analysis Set

The efficacy analysis set will consist of all subjects who received at least 1 dose of romiplostim. The analyses of all efficacy endpoints will be based on the efficacy analysis set.

10.1.2.4 Per Protocol Analysis Set

The per protocol analysis set will consist of all subjects who received at least 1 dose of IP and met all eligibility criteria. A sensitivity analysis using the per protocol set will be conducted for the primary efficacy endpoint.

10.2 Sample Size Considerations

The sample size for this study is governed by the number of pediatric ITP subjects who meet the eligibility requirements during enrollment period. It is estimated that approximately 200 subjects will enroll into this study. The percentage of time achieving platelet response in the first 6 months of treatment period for ITP subjects with romiplostim (both adults and pediatric) is estimated at 74%. The standard deviation of percentage of time is estimated between 30% and 36% based on previous Nplate data. Given the sample size of 200 subjects, the half width of the 95% confidence interval (CI) for the percentage of time achieving platelet response is estimated to be between 4% and 5%.

10.3 Planned Analyses

The analysis will be descriptive in nature. No formal hypothesis is to be tested.

10.3.1 Interim Analyses

Interim analyses will be conducted to support regulatory filings, and accumulated data for this study will be summarized to provide ongoing assessments of the safety of romiplostim. These interim analyses will occur at least annually until the end of the study.

10.3.2 Analysis of Key Study Endpoints

10.3.2.1 Efficacy Endpoints

The primary endpoint for this study is the percentage of time with platelet response starting from week 2 in the first 6 months of the treatment period. Platelet response is defined as platelet count $\geq 50 \times 10^9/L$ at a scheduled protocol visit. Platelet counts within 4 weeks of a rescue ITP medication will not be deemed as platelet response. The 95% CI will be calculated for the estimated percentage of time.

Summary statistics of platelet counts and responses will be provided at weeks 1 to 8 and then every 4 weeks.

The percentage of time with platelet response starting from week 2 until the EOT period will be summarized with 95% CI.

Product: Romiplostim
Protocol Number: 20101221
Date: 15 August 2014

Page 48 of 69

Missing platelet counts at weeks 12 and 16, and every 4 weeks thereafter will be imputed by using the mean of the 2 closest non-missing platelet counts within ± 1 week before study discontinuation. If still missing after imputation, platelet counts will be considered as non-response.

The proportion of subjects with splenectomy during the study will be summarized for the subjects who entered this study without splenectomy.

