7.1 Schedule of Assessments

The Schedule of Assessments is found in [Table 2](#) below.

Table 2. Schedule of Assessments

Procedures	Screening	In Clinic Dosing Period ^a	Romiplostim Treatment Period (up to 36-months) ^b			End Of Treatment Visit	End of Study Visit
	- 4 Weeks	Week 1 to Week 8	Weekly	Every 4 Weeks	Every 12 Weeks		
Informed consent	X						
Confirmation of primary ITP diagnosis	X						
ITP/medical history	X						
Physical exam	X				X	X	
Vital signs	X				X	X	
Weight	X				X		
Central lab CBC with differential	X	X ^c		X ^b		X	
Central lab blood (serum) chemistry	X				X	X	
Local lab platelet counts	X	X	X ^{b,d}			X	X
Local lab peripheral blood smear		X ^c		X ^b		X	
Pregnancy test	X				X ^f	X ^f	
Concomitant /rescue medications	X	X	X	X	X	X	X
Adverse event reporting		X	X	X	X	X	
Serious adverse events	X	X	X	X	X	X	X
Antibody sample ^e		Day 1 (before first dose)			W12, W52 and every 24 weeks thereafter	X	
Romiplostim dosing		X	X				

ITP = immune thrombocytopenia; CBC = complete blood counts

- ^a Week 1 to Week 8. All subjects will return to the clinic for weekly dosing of romiplostim, platelet counts by a local laboratory, recording of concomitant/rescue medications, and adverse event reporting.
- ^b Subjects who complete 6 months of sustained platelet response (platelet count $\geq 50 \times 10^9/L$ in the absence of romiplostim or any ITP medications) will have assessments every 12 weeks for the duration of the 36-month treatment period.
- ^c Central CBC with differential and local lab peripheral blood smears are to be performed every 4 weeks, including pre-dose at week 1. Screening laboratory studies may be used in lieu of the pre-treatment day 1 week 1 laboratory tests if performed within 10 days prior to the first dose. Bone marrow biopsy suggested if abnormalities detected.
- ^d For subjects who establish a stable dose of romiplostim and are self-administering, have the injection administered by a caregiver, or meet this criterion but still prefer to come to the clinic for romiplostim administration, platelet counts will be monitored every 4 weeks.
- ^e For subjects who test positive for antibodies, see [Section 7.1.3](#). Antibody sampling during romiplostim treatment is only conducted if subject is receiving study drug.
- ^f Local lab urine or serum pregnancy test for female subjects of child-bearing potential (defined as having first menses)

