#### 4.3 Secondary Endpoints

- The percentage of time with platelet response starting from Week 2 until the end of the treatment (EOT) period.
- For each subject, the percentage of time with a platelet response from Week 2 till EOT is calculated as the number of weeks with a platelet response divided by the total number of weeks. Weekly platelet counts are imputed by last observation carry forward using rescue-evaluable weekly platelet counts during the treatment period.
- Descriptive statistics (n, mean, standard deviation, median, Q1 [25th percentile], Q3 [75th percentile], minimum, and maximum) are provided for the average percentage of time across subjects.
- The percentage of time with an increase in platelet count  $\geq 20 \times 10^9/L$  above baseline starting from Week 2 until the end of the treatment period without rescue medication use for ITP in the past 4 weeks.
- For each subject, the percentage of time with an increase in platelet count  $\geq 20 \times 10^9/L$  above baseline from Week 2 till EOT is calculated as the number of weeks with an increase in platelet count  $\geq 20 \times 10^9/L$  above baseline divided by the total number of weeks. Weekly platelet counts are imputed by last observation carry forward using rescue-evaluable weekly platelet counts during the treatment period.
- Descriptive statistics (n, mean, standard deviation, median, Q1 [25th percentile], Q3 [75th percentile], minimum, and maximum) are provided for the average percentage of time across subjects.
- Subject incidence of rescue ITP medications used.
- Total number and percentage of subjects who reported any usage of rescue medications for ITP are calculated with a sub-categorization by preferred terms.
- The incidence of anti-romiplostim neutralizing antibodies and cross reactive antibodies to TPO at any time during the study.
- Number and percentage of subjects who developed anti-romiplostim neutralizing antibodies and/or cross reactive antibodies to TPO by study visits are calculated.
- The incidence of adverse events, including clinically significant changes in laboratory values.

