### **10.5 Efficacy Analyses**

The efficacy analysis will be based on the Efficacy Analysis Set, which includes all subjects who receive at least one dose of romiplostim.

Summary statistics of platelet counts and responses will be provided weekly at Week 1 to 8 and then every 4 weeks for all subjects in the efficacy analysis set and by age groups (<6, 6-<12, 12-<18 years). Platelet response is defined as platelet count

---

$\geq 50 \times 10^9/L$ . Platelet counts within 4 weeks after rescue medication use will not be deemed as platelet responses.

The percentage of time with platelet response starting from Week 2 in the first 6 months of the treatment period will be estimated for all treated subjects and by age groups (<6, 6-<12, 12-<18).

The percentage of time with platelet response from Week 2 till the end of the treatment period will be estimated for all treated subjects and by age groups (<6, 6-<12, 12-<18).

The percentage of time with an increase in platelet counts  $\geq 20 \times 10^9/L$  above baseline starting without rescue medication use during past 4 weeks from Week 2 until the end of the treatment period will be estimated for all treated subjects and by age groups (<6, 6 <12, 12-<18).

The proportion of subjects who used rescue medication for ITP during the study will be summarized by preferred terms. Rescue medication is defined as any medication or transfusion, other than romiplostim and excluded medications, that is administered after enrollment to the subject during screening or throughout the treatment period with the intent of raising platelet counts or prevent bleeding and includes concomitant medications for ITP where the dose and/or schedule is increased.

The proportion of subjects who achieved sustained platelet response for 24 weeks or longer will be summarized. A sustained platelet response is defined as a platelet count  $\geq 50 \times 10^9/L$  without the use of any ITP medications.

The proportion of subjects who had a splenectomy during the study will be summarized for the subjects who entered this study without splenectomy.

Number and percentage of subjects who started self-administration of romiplostim during the study will be summarized.

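### As written, the by-visit imputation rule scores drug-free responders on the 12-weekly schedule as non-responders at 4-weekly points when no count was due

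*Protocol*

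**What the plan says.** Protocol 10.3.2.1 sets the reporting grid: "Summary statistics of platelet counts and responses will be provided at weeks 1 to 8 and then every 4 weeks". SAP 10.5 keeps it for all subjects in the efficacy analysis set and by age group: "Summary statistics of platelet counts and responses will be provided weekly at Week 1 to 8 and then every 4 weeks".

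The rule for gaps is in the same protocol section. "Missing platelet counts at weeks 12 and 16, and every 4 weeks thereafter will be imputed", using "the mean of the 2 closest non-missing platelet counts within ± 1 week before study discontinuation". The fallback is "If still missing after imputation, platelet counts will be considered as non-response". No group of subjects is exempted.

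The visit schedule is not the same for all children. Under Protocol Table 2 footnote b, those who complete 6 months of sustained response without romiplostim or other ITP medication "will have assessments every 12 weeks for the duration of the 36-month treatment period". Section 7.6 confirms that platelet counts are among the procedures that become 12-weekly. During the first 6 months of such a response the ordinary schedule still applies (Sections 3.1.1 and 7.6).

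The SAP has no imputation rule for the by-visit summaries. Its Section 9.3 lists missing platelet counts among the data that need imputation and refers the algorithm to the Data Definition Table. For the percentage-of-time endpoints to end of treatment, SAP 4.3 uses another method: "Weekly platelet counts are imputed by last observation carry forward using rescue-evaluable weekly platelet counts during the treatment period". SAP Section 6 ends the treatment period one week after the last dose. SAP Section 11 reports no departure from the protocol.

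**The concern.** Scoring a missing value as non-response is sensible when a visit was due and the child did not attend. Here the protocol itself removes the visits because the child is doing well, and the imputation rule then reads the resulting gap as failure. The error depends on the schedule, not on chance, and it falls only on children with a lasting response off all ITP medication.

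Visits are counted from day 1 (Protocol Section 7), so the off-schedule weeks coincide across these children. The long-term by-visit response rate would then dip at those weeks and recover at each 12-weekly visit, for reasons unrelated to platelet counts. The study is descriptive, so such tables are results in their own right. Interim summaries to support regulatory filings are planned at least annually (Protocol 10.3.1, SAP Section 8) and could carry the same artefact.

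**Working it through.** **The plan's own figure.** Protocol 10.2 gives a 95% CI half-width of 4% to 5% for N = 200 and SD 30% to 36%. Half-width = 1.96 × SD / √200: 1.96 × 30 / √200 = 4.16 and 1.96 × 36 / √200 = 4.99. The figure reproduces. It applies to percentage of time in the first 6 months, not to later by-visit rates.

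**Inputs for the check.**
- Analysis points: every 4 weeks from week 12 (Protocol 10.3.2.1).
- Fill window: ±1 week, using the two closest counts (same section).
- Count interval after 6 months of drug-free response: 12 weeks (Table 2 footnote b; Section 7.6).
- Visits anchored on day 1 (Section 7); platelet counts from local laboratories only (Section 7.1.2).

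**One child, one cycle.** Take consecutive counts at weeks w and w + 12, both at or above 50 × 10⁹/L. The intermediate points are w + 4 and w + 8. Each is 4 weeks from its nearest count, outside ±1 week, so neither can be filled and both become non-response. That is 2 of every 3 points.

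**Enumeration over weeks 40 to 144** (27 points, every observed count at or above the threshold):
- Visits on the 4-weekly grid: 18 of 27 scored non-response (66.7%).
- Visits 1 week or more off the grid, two counts required in the window: 27 of 27.
- Visits off the grid, one count accepted: 18 of 27, or 27 of 27 when the visit falls 2 weeks from the nearest points.

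Two of three is therefore the minimum over complete 12-week cycles.

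**Whole remission.** The first 26 weeks on the ordinary schedule are not lost, so the share over the entire drug-free period to week 156 is smaller:
- Off drug from week 12: 20 of 37 points (54%).
- From week 52: 13 of 27 (48%).
- From week 104: 4 of 14 (29%).

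**Effect on the by-visit rate.** Let p be the share of subjects on the 12-weekly schedule, all truly responding. At off-schedule weeks the reported rate is the true rate minus p. The documents do not give p. As an illustration only, borrow 74% (the protocol's estimate for the first 6 months) as the true rate:
- p = 5%: 74 − 5 = 69%.
- p = 10%: 74 − 10 = 64%.
- p = 20%: 74 − 20 = 54%.

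**Dropping these children from the denominator instead.** The rate becomes (74 − p) / (100 − p):
- p = 10%: 64/90 = 71.1%, still 2.9 points low.
- p = 20%: 54/80 = 67.5%, still 6.5 points low.

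**The case against.** The best reply is that a count not due is not missing. Protocol 10.3.2.1 ties response to a scheduled visit, Section 7 treats missed visits as events to be explained in source records, and SAP 9.3 sends the algorithm to a Data Definition Table that is not among the documents. The programmed rule may therefore be sensible. This makes mis-scoring less certain in practice. It does not remove the point, because the protocol lists the time points for everyone without exception and neither document states the milder reading.

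The second reply is that little depends on these tables, and much of that stands. Twelve-weekly visits cannot start before about week 26, so the first-6-month endpoint is essentially untouched. Sustained response off all ITP medication has its own exploratory endpoint (Protocol 10.1.1, SAP 4.4), so a reader who concludes that the study records remission as failure goes too far. The SAP definitions of the primary and percentage-of-time endpoints (4.2, 4.3) do not use the ±1 week rule.

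A reader might also infer that the documents give the same child opposite scores: 33% under the protocol rule and 100% under SAP carry-forward. They do not show this. Carry-forward runs only within a treatment period that the SAP closes one week after the last dose, so the weeks of a lasting drug-free response fall outside it unless dosing resumes. A by-visit table and a per-child percentage of time are also different outputs.

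**Conclusion.** The point holds for the later by-visit response summaries. Read literally, Protocol 10.3.2.1 turns at least two of three 4-weekly points per complete 12-week cycle into non-response for children who have finished 6 months of drug-free response, even when all their observed counts meet the threshold. The SAP retains the table and does not replace the rule.

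The understatement at off-schedule weeks is at most the share of subjects on the 12-weekly schedule. The 5% to 20% range is an assumption. The documents also do not support a claim that the error must grow with follow-up, since that depends on how many children enter this phase and how many resume dosing. Nor should the shortfall be judged against the planned 4 to 5 point half-width, which belongs to an endpoint that this rule barely reaches. The matter deserves correction because the error is systematic and cheap to remove, not because it threatens the primary result.

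**What to change.** Add a by-visit rule to the SAP:
- A 4-weekly point not due under the 12-weekly schedule is not missing.
- At such a point, carry response between two consecutive scheduled counts at or above 50 × 10⁹/L with no ITP medication in between.
- Apply non-response only to visits that were due and missed.

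Do not drop these children from the denominator at off-schedule weeks. That removes known responders and leaves a smaller downward bias and dip.

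Record the change in SAP Section 11, align the Data Definition Table with it, and reconcile the SAP's treatment-period definition with the protocol's 36-month treatment period for these tables. The cost is SAP wording and a schedule flag in the derivation; no new visits or data are needed.

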10.3.2.2 Safety Endpoints

The exposure-adjusted incidence rates as well as subject incidence rates of adverse events will be summarized by system organ class and by preferred term according to the MedDRA dictionary. Exposure-adjusted rate is defined as total number of events divided by time of duration when subjects were under observation. The summary includes all treatment-emergent adverse events recorded from the start of IP on this study, or any worsening of conditions present at baseline before dosing in this study. This summary for adverse events will be performed for the following categories

- all adverse events
- romiplostim-related adverse events
- serious adverse events
- adverse events leading to withdrawal from the study
- adverse events of interest (hemorrhage events, etc.)

In addition, incidence and exposure-adjusted rates of adverse events by period may also be explored.

Subject listings for all adverse events, serious adverse events, and adverse events leading to withdrawal from the study will be provided.

The incidence and percentage of subjects who develop anti-romiplostim antibodies (binding and if positive, neutralizing) at any time will be tabulated.

Summary statistics will be provided for blood chemistry and CBC at each time point. Shift tables between the worst post-baseline and baseline values will be provided (based on the National Cancer Institute CTCAE, version 3.0).

10.3.3 Primary Analysis

The objective for the primary analysis will be to summarize the data with the respect to the primary and secondary endpoints for the trial. The primary analysis will occur after the last subject has completed all investigational treatment and observations on this protocol. The primary analysis will serve as the final analysis for the trial.

Product: Romiplostim
Protocol Number: 20101221
Date: 15 August 2014

Page 49 of 69

10.3.4 Additional Analyses

10.3.4.1 Subject Accountability

The number of subjects who enrolled into the study, received at least 1 dose of IP, completed the IP, completed the study and prematurely withdrew, and the reason for premature withdrawal, will be summarized.

10.3.4.2 Demographic and Baseline Characteristics

Demographics and selected current study baseline characteristics will be summarized using descriptive statistics and listed for the following:

- age, sex, and race
- height, weight
- medical history
- ITP history
- baseline hematology
- baseline physical examination
- baseline vital signs

10.3.4.3 Investigational Product Administration

Summary statistics will be provided for cumulative dose (by μg and $\mu\text{g}/\text{kg}$) and average weekly dose (by $\mu\text{g}/\text{week}$ and $\mu\text{g}/\text{kg}/\text{week}$). Exposure summary by baseline splenectomy status (yes/no) and concurrent ITP therapy status will also be provided. Weekly summary for weight-based dose will also be provided.

A listing of IP administration, including weight-based dose and reason for ending IP will be provided.

11. REGULATORY OBLIGATIONS

11.1 Informed Consent

An initial sample informed consent form is provided for the investigator to prepare the informed consent document to be used at his or her site. Updates to the template will be communicated by letter from the Amgen Clinical Study Manager to the investigator. The written informed consent documents should be prepared in the language(s) of the potential subject population.

If the subject is \geq age 7 but has not attained the legal age for consent for treatments or procedures involved in clinical investigations, under the applicable law of the jurisdiction in which the clinical investigation will take place, the investigator is responsible for

Product: Romiplostim
Protocol Number: 20101221
Date: 15 August 2014

Page 50 of 69

obtaining written assent from the subject. For specific local information, consult the country-specific requirements of the applicable countries.

Before a subject's participation in the clinical study, the investigator is responsible for obtaining written informed consent and assent (if applicable) from the subject and/or legally acceptable representative after adequate explanation of the aims, methods, anticipated benefits, and potential hazards of the study and before any protocol-specific screening procedures or any IP is administered. A legally acceptable representative is an individual or other body authorized under applicable law to consent, on behalf of a prospective subject, to the subject's participation in the clinical study.

The investigator is also responsible for asking the subject or his/her legally acceptable representative if the subject has a primary care physician and if the subject agrees to have his/her primary care physician informed of the subject's participation in the clinical study. If the subject or his/her legally acceptable representative agrees to such notification, the investigator shall inform the subject's primary care physician of the subject's participation in the clinical study. If the subject does not have a primary care physician and the investigator will be acting in that capacity, the investigator should document such in the subject's medical record.

The acquisition of informed consent and, if applicable, assent and the subject's agreement or refusal of his/her notification of the primary care physician is to be documented in the subject's medical records, and the informed consent/assent form should be signed and personally dated by the subject or a legally acceptable representative and by the person who conducted the informed consent discussion. The original signed informed consent form and assent form, if applicable, should be retained in accordance with institutional policy, and a copy of the signed consent form/assent form should be provided to the subject or legally acceptable representative.

If a potential subject is illiterate or visually impaired and does not have a legally acceptable representative, the investigator must provide an impartial witness to read the informed consent form/assent form to the subject and must allow for questions.

Thereafter, both the subject and the witness must sign the informed consent form/assent form to attest that informed consent was freely given and understood.

